## **7.0 TRIAL PROCEDURES**

### **7.1 Trial Procedures**

The Trial Flow Chart - Section 6.0 summarizes the trial procedures to be performed at each visit. Individual trial procedures are described in detail below. It may be necessary to perform these procedures at unscheduled time points if deemed clinically necessary by the investigator.

#### **7.1.1 Administrative Procedures**

##### **7.1.1.1 Informed Consent**

The Investigator must obtain documented consent from each potential subject prior to participating in a clinical trial.

##### **General Informed Consent**

Consent must be documented by the subject's dated signature or by the subject's legally acceptable representative's dated signature on a consent form along with the dated signature of the person conducting the consent discussion.

A copy of the signed and dated consent form should be given to the subject before participation in the trial.

The initial informed consent form, any subsequent revised written informed consent form and any written information provided to the subject must receive the IRB/ERC's approval/favorable opinion in advance of use. The subject or his/her legally acceptable representative should be informed in a timely manner if new information becomes available that may be relevant to the subject's willingness to continue participation in the trial. The communication of this information will be provided and documented via a revised consent form or addendum to the original consent form that captures the subject's dated signature or by the subject's legally acceptable representative's dated signature.

The informed consent will adhere to IRB/ERC requirements, applicable laws and regulations and Sponsor requirements.

##### **7.1.1.2 Inclusion/Exclusion Criteria**

All inclusion and exclusion criteria will be reviewed by the investigator or qualified designee to ensure that the subject qualifies for the trial.

##### **7.1.1.3 Medical History**

A medical history will be obtained by the investigator or qualified designee. Medical history will include all active conditions, and any condition diagnosed within the prior 10 years that are considered to be clinically significant by the Investigator. Details regarding the disease for

which the subject has enrolled in this study will be recorded separately and not listed as medical history.

#### **7.1.1.4 Prior and Concomitant Medications Review**

##### **Prior Medications**

The investigator or qualified designee will review prior medication use, including any protocol-specified washout requirement, and record prior medication taken by the subject within 28 days before starting the trial. Treatment for the disease for which the subject has enrolled in this study will be recorded separately and not listed as a prior medication.

##### **Concomitant Medications**

The investigator or qualified designee will record medication, if any, taken by the subject during the trial. All medications related to reportable SAEs and ECIs should be recorded as defined in Section 7.2.

#### **7.1.1.5 Disease Details and Treatments**

##### **Disease Details**

The investigator or qualified designee will obtain prior and current details regarding disease status.

##### **Prior Treatment Details**

The investigator or qualified designee will review all prior cancer treatments including systemic treatments, radiation and surgeries.

##### **Subsequent Anti-Cancer Therapy Status**

The investigator or qualified designee will review all new anti-neoplastic therapy initiated after the last dose of trial treatment. If a subject initiates a new anti-cancer therapy within 30 days after the last dose of trial treatment, the 30 day Safety Follow-up visit must occur before the first dose of the new therapy. Once new anti-cancer therapy has been initiated the subject will move into survival follow-up.

#### **7.1.1.6 Trial Compliance (Medication/Diet/Activity/Other)**

Compliance with XL888 will be determined using drug diary and pill counts performed on day 1 of each cycle. Patients who take less than 80% of their prescribed dose of pembrolizumab and/or XL888 due to reasons other than toxicity will be considered inevaluable for the primary endpoint of toxicity and will be replaced.

## **7.1.2 Clinical Procedures/Assessments**

### **7.1.2.1 Adverse Event (AE) Monitoring**

The investigator or qualified designee will assess each subject to evaluate for potential new or worsening AEs as specified in the Trial Flow Chart and more frequently if clinically indicated. Adverse experiences will be graded and recorded throughout the study and during the follow-up period according to NCI CTCAE Version 4.0 (see Section 11.2). Toxicities will be characterized in terms regarding seriousness, causality, toxicity grading, and action taken with regard to trial treatment.

For subjects receiving treatment with pembrolizumab all AEs of unknown etiology associated with pembrolizumab exposure should be evaluated to determine if it is possibly an event of clinical interest (ECI) of a potentially immunologic etiology (termed immune-related adverse events, or irAEs). .

Please refer to section 7.2 for detailed information regarding the assessment and recording of AEs.

Winship Cancer Institute's Clinical Trials Office will perform the quality assurance and quality control checks on this clinical trial. Before enrollment of any subject in this study, CTO personnel and the Investigator will review the protocol; the Investigator's Brochure; the CRFs/electronic CRFs and instructions for completion; the informed consent process; and the procedure for reporting AEs and SAEs.

### **7.1.2.2 Full Physical Exam**

The investigator or qualified designee will perform a complete physical exam during the screening period. Clinically significant abnormal findings should be recorded as medical history. A full physical exam should be performed during screening,

### **7.1.2.3 Directed Physical Exam**

For cycles that do not require a full physical exam per the Trial Flow Chart, the investigator or qualified designee will perform a directed physical exam as clinically indicated prior to trial treatment administration.

### **7.1.2.4 Vital Signs**

The investigator or qualified designee will take vital signs at screening, prior to the administration of each dose of trial treatment and at treatment discontinuation as specified in the Trial Flow Chart (Section 6.0). Vital signs should include temperature, pulse, respiratory rate, weight and blood pressure. Height will be measured at screening only.

#### **7.1.2.5 Eastern Cooperative Oncology Group (ECOG) Performance Scale**

The investigator or qualified designee will assess ECOG status (see Section 11.1) at screening (within 10 days of day 1 cycle 1), prior to the administration of each dose of trial treatment and discontinuation of trial treatment as specified in the Trial Flow Chart.

#### **7.1.2.6 Tumor Imaging and Assessment of Disease: Response Evaluation Criteria in Solid Tumors (RECIST) 1.1 Criteria for Evaluating Response in Solid Tumors**

RECIST version 1.1\* will be used in this study for assessment of tumor response. While either CT or MRI may be utilized, as per RECIST 1.1, CT is the preferred imaging technique in this study.

#### **7.1.2.7 Tumor Tissue Collection and Correlative Studies Blood Sampling**

Pre- and post- treatment tumor biopsies will be obtained from 16 patients enrolled on the expansion phase. Patients will sign the optional biopsy consent prior to starting treatment and will be assigned to either start pembrolizumab or pembrolizumab/XL888 for the first cycle. Biopsies will be obtained within 4 weeks prior to the first dose of study therapy (biopsy #1) and then during the third week between Day 14 and Day 20. At least three core biopsies will be obtained at the time of the biopsy (unless limited for technical/safety reasons). The obtained tissues will be handled in the following way:

- 1) RNAlater for RNA stabilization and tissue storage
- 2) Formalin-fixed paraffin block with one cut H&E stained slide
- 3) Liquid nitrogen frozen tissue in cryo-preservation vials

All collected tissues are stabilized and stored in -80°C freezers (RNAlater stabilized, OCT embedded, short term storage) or the vapor phase of a liquid nitrogen freezer (long term storage) in single use aliquots. All FFPE tissue blocks are stored in a climate controlled storage room that is temperature (less than 27°C) and humidity controlled.

Tissue will be evaluated using IHC for CD3, CD4, CD8, CD163, PD-1, PD-2, PDL-1, MIF, TAM and stromal/ vascular markers. Tissue will also be dissociated and flow cytometry will be used to determine the characteristics of macrophages and lymphocytes. Genomic (transcriptome) profiling will be performed on tissue and lymphocytes.

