## 2.0 TRIAL DESIGN

Open label phase I trial. Primary objective is to determine the recommended phase 2 dose (RP2D) of the combination of XL888 and pembrolizumab. The design is 3+3 with 3 dose levels of XL888 (X). MTD is defined as the dose at which less than one-third of the subjects experience a DLT in the first 4 weeks of treatment.

After determining the RP2D, an additional 16 patients with pancreatic cancer (Arm A) and 16 patients with colorectal cancer (Arm B) will be enrolled in an expansion phase to confirm toxicity profile and obtain paired biopsies. Paired biopsy performed on 8 patients in each group. Patient selected for biopsy must have a primary or metastatic non-bone site that is amenable to safe biopsy. Bone only lesions are not suitable for biopsy. Patients undergoing paired biopsies will be assigned into two treatment cohorts (8 in each) and treated according to the schema below.

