#### **4.2.1 Rationale for Endpoints**

- 4.2.1.1 Efficacy Endpoints:** This is a phase I trial. The primary endpoint is still toxicity. The plan is to evaluate the response rate, response duration, and progression free

survival of the patients on the trial. These endpoints will provide preliminary data in two patient subsets: patients with pancreatobiliary and other GI malignancies.

- 4.2.1.2 **Biomarker Research:** We intend in all patients to evaluate the effects of the combination on T-cell population in peripheral blood. In addition, we plan to evaluate the effects of the combination versus pembrolizumab alone in paired biopsy samples in 16 patients. These samples will be analyzed for tumor infiltrating lymphocytes, stromal/tumor markers and expression immune inhibitory molecules (PD-L1, PD-L2, PD1, etc). We anticipate to see a difference between the group treated with the combination versus the group treated with pembrolizumab alone.

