## 5.2 Trial Treatments

The treatment to be used in this trial is outlined below in Table 2

Table 2 Trial Treatment

Drug	Dose/Potency	Dose Frequency	Route of Administration	Regimen/Treatment Period
Pembrolizumab	200 mg	Q3W	IV infusion	Day 1 of each 3 week cycle
XL888	As Below	Twice weekly (Days 1 and 4)	Oral	Twice weekly (days 1 and 4) cycle is 3 weeks

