### **5.3.3 Timing of Dose Administration**

Trial treatment should be administered on Day 1 of each cycle after all procedures/assessments have been completed as detailed on the Trial Flow Chart (Section 6.0). Trial treatment may be administered up to 3 days before or after the scheduled Day 1 of each cycle due to administrative reasons.

All trial treatments will be administered on an outpatient basis.

**Pembrolizumab** 200 mg will be administered as a 30 minute IV infusion every 3 weeks. Given the variability of infusion pumps, a window of -5 minutes and +10 minutes is permitted (i.e., infusion time is 30 minutes: -5 min/+10 min).

The Pharmacy Manual contains specific instructions for the preparation of the pembrolizumab infusion fluid and administration of infusion solution.

**XL888** will be administered twice weekly (days 1 and 4) orally starting on day 1 of every 3-week cycle.

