#### **7.1.4.3 Between days 14-21 cycle 1**

- Repeat biopsy in selected cases.

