## **8.0 STATISTICAL ANALYSIS PLAN**

### **8.1 Determination of Sample Size**

This is a 3+3 standard phase I trial design. The plan is to evaluate two dose cohorts- 45mg and 90 mg. An intermediate dose cohort (60 mg) will be evaluated only if we observe 2 or more DLT's in the 3 or 6 patients enrolled on the 90mg dose. If we observe 2 dose limiting toxicities on dose level 1, then the study will be completed with three patients (minimal number of patients). If we observe two DLT in the first three patients on dose level 1, the study will stop and the principal investigator will discuss at that point whether a lower dose level of XL888 should be tested. If we do not observe any dose limiting toxicities the study will require 9 patients. If we observe one dose limiting toxicity per dose level (maximum number of patient), then the study would require 18 patients. Therefore the phase part sample size can range from 3 to 18 patients. Expansion phase will be started once the recommended phase II dose (RP2D) is determined. Given minimal activity of checkpoint inhibitors in colorectal and pancreatic cancer, an overall response rate of the combination of PD-1 plus HSP90 inhibitor of 20% would be considered clinically significant. With an alpha of 0.1, and power of 80% (relaxed due to the pilot preliminary nature of this proposal) a total of 16 patients should be sufficient to make this determination. We will also obtain biologic endpoints with the paired biopsy samples that can help further develop the combination and understand its role in GI cancers. We plan to enroll 32 patients on the RP2D level with 16 patients per cohort (pancreas and colorectal cancer). Patients in the expansion phase will be assigned to treatment arms by PI (MK-3475 or MK-3475 plus XL-888). After the first 3 weeks all patients will receive the combination therapy. There is no planned comparison between the two arms. The aim of the expansion phase is to confirm the safety profile and tolerability of the regimen in patients with pancreatic and colorectal cancer.

The total number of patients will range from 38 to 50 patients.

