### **8.4 Analysis Sets**

All subjects who receive any amount of study drug will be included in the evaluation of safety and efficacy, except for patients who take less than 80% of their prescribed dose of pembrolizumab and/or XL888 since they will be considered inevaluable for the primary endpoint of toxicity.

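### Section 8.1 conflicts with 2.0 and 7.1.2.7 on who starts with pembrolizumab alone, and lead-in data are not separated in the analysis; separately, the second-biopsy window overlaps the earliest allowed start of cycle 2

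*Combined protocol and SAP*

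**What the plan says.** **Who is assigned.** Section 2.0 says: "Patients undergoing paired biopsies will be assigned into two treatment cohorts (8 in each" cohort). Section 7.1.2.7 likewise ties the choice of first-cycle treatment to patients who sign the optional biopsy consent. The Day 1 visit list in 7.1.4.2 holds XL888 in cycle 1 only in selected paired-biopsy patients. Section 8.1 has no such limit: "Patients in the expansion phase will be assigned to treatment arms by PI (MK-3475 or MK-3475 plus XL-888"), with everyone on the combination after three weeks.

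**What the contrast is for.** Section 4.2.1.2 plans to "evaluate the effects of the combination versus pembrolizumab alone in paired biopsy samples in 16 patients".

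**How the data are analysed.** Section 8.4 begins: "All subjects who receive any amount of study drug will be included in the evaluation of safety and efficacy". The same sentence then excepts patients who take under 80% of the prescribed pembrolizumab and/or XL888. Sections 8.3 and 8.6 describe summaries of toxicity, activity and adverse events without separating the lead-in cycle.

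**Timing.** Section 7.1.2.7 sets the second biopsy "then during the third week between Day 14 and Day 20"; the visit list, under 7.1.4.3, gives "Between days 14-21 cycle 1". Section 5.2 gives pembrolizumab on "Day 1 of each 3 week cycle". Section 5.3.3 adds: "Trial treatment may be administered up to 3 days before or after the scheduled Day 1 of each cycle due to administrative reasons". The Day 1 visit list gives the first XL888 dose of each cycle on Day 1, before pembrolizumab.

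**The concern.** Here, lead-in patients are those whose first cycle is pembrolizumab alone. The two points about them have different consequences.

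First, the plan gives two answers on which expansion patients lack XL888 in cycle 1. Section 8.1 says the expansion is meant to confirm the regimen's safety and tolerability, and secondary objectives A and B concern the combination's toxicity and activity. A lead-in patient contributes 21 days without XL888, and one who stops in that period contributes no XL888 exposure at all. If such data are pooled unmarked, the combination's tables describe something other than the combination. A lead-in without a biopsy, which 8.1 permits, would also yield no tissue for the contrast that motivates the lead-in.

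Second, the paired-biopsy contrast is the trial's only direct look at what XL888 adds in tumour. A lead-in biopsy taken after the first XL888 dose is no longer a pembrolizumab-alone sample. With 8 patients in the group, one misclassified sample is 1/8 = 12.5% of it.

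**Working it through.** **A. Assignment**

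The plan's counts reproduce: 16 pancreatic + 16 colorectal = 32 expansion patients; 8 + 8 = 16 biopsy patients; 18 + 32 = 50, the upper total.

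| Section | Who is assigned a first-cycle treatment | Pool |
|---|---|---|
| 2.0 | Paired-biopsy patients, 8 per treatment cohort | 16 of 32 |
| 7.1.2.7 | Patients signing the biopsy consent | 16 of 32 |
| 7.1.4.2, Day 1 list | XL888 held in selected biopsy patients | within the 16 |
| 8.1 | Expansion patients, no restriction | 32 of 32 |

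Starters on pembrolizumab alone: 8/32 = 25% under 2.0. Under 8.1 the number is not given; an equal split, which is only an assumption, would make it 16/32 = 50%.

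**B. Route into the analysis**

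Take a lead-in patient who receives the cycle 1 infusion and stops before cycle 2.

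- Pembrolizumab: 1 dose prescribed, 1 taken, 100%.
- XL888: 0 prescribed, 0 taken. The ratio 0/0 is undefined.

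The under-80% exception in 8.4 therefore does not clearly apply, while the any-study-drug rule does. Sections 5.7.2 and 7.1.1.6 replace patients only when the reason is not toxicity, and they concern evaluability for the primary endpoint. Neither says that a replaced patient leaves the safety and activity summaries. A lead-in patient who stops for toxicity is not replaced under either.

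For patients who do cross over, the effect on response is limited. The first on-study scan is due from cycle 3 Day 15, which is Day 2 × 21 + 15 = 57. XL888 starts nominally on Day 22, so 57 − 22 = 35 days of combination come before it. The parts most exposed are cycle 1 toxicity and patients who never take XL888.

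**C. Biopsy timing**

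Days are counted from the first dose as Day 1, consistent with the XL888 days 1, 4, 8, 11, 15 and 18 in the visit list.

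- Nominal cycle 2 Day 1 = 1 + 21 = Day 22.
- Allowed start = 22 − 3 to 22 + 3 = Days 19 to 25.
- Window in 7.1.2.7 (Days 14–20): overlap on Days 19 and 20, 2 of 7 days. The longest lag after XL888 is 20 − 19 = 1 day.
- Window in the visit list (Days 14–21): overlap on Days 19, 20 and 21, 3 of 8 days. The longest lag is 21 − 19 = 2 days.
- Nominal schedule: no overlap, since both windows close before Day 22.

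To gauge size, assume biopsy day *b* and cycle 2 day *c* are independent and uniform over their windows. The documents give no distribution.

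| Window | Pairs | *b* > *c* | Expected of 8 | *b* ≥ *c* | Expected of 8 |
|---|---|---|---|---|---|
| Days 14–20 | 7 × 7 = 49 | 1/49 = 2.0% | 0.16 | 3/49 = 6.1% | 0.49 |
| Days 14–21 | 8 × 7 = 56 | 3/56 = 5.4% | 0.43 | 6/56 = 10.7% | 0.86 |

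**The case against.** The strongest reply is that the intended order is clear. The visit list labels the repeat biopsy a cycle 1 procedure. The flow chart appears to mark tissue collection at screening and cycle 1 only. Section 5.3.3 puts Day 1 dosing after the flow-chart procedures, and 8.1 starts the combination after three weeks. A misplaced sample needs cycle 2 brought forward for administrative reasons and the biopsy taken after that dose. This stands, and it also favours the lower percentages, because same-day biopsies should precede dosing. What remains is that no sentence fixes the order for this biopsy or says how a late sample is classed, and that the two windows differ by a day.

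On assignment, three places agree and 8.1 may simply be loose wording; the diagram in 2.1 is not in the text available here and may settle it. That is fair, but 8.1 is the statistical section and as written it contradicts the others.

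The biopsy contrast is also exploratory, 8.3 plans no formal testing, and 8.1 disclaims a comparison between arms. This limits the stakes.

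A reader might go further and infer three things that the documents do not support:

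- That the lead-in is not kept separate from the combination. It is separate on the nominal schedule.
- That the assignment conflict contaminates biopsies. It changes who lacks XL888 in cycle 1, not what is in a lead-in sample.
- That 8.4 expressly counts a never-XL888 patient as a combination patient. It does not say so, and it carries the under-80% exception; the gap is that the exception does not clearly reach such a patient.

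**Conclusion.** Both points hold, as separate matters, and should be corrected. Neither calls the dose-finding into question.

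The assignment conflict is the more important. It leaves the number without XL888 in cycle 1 at 8 of 32 by 2.0 and unspecified by 8.1. Followed as written, 8.3, 8.4 and 8.6 put pembrolizumab-only cycle 1 data, and possibly patients who never took XL888, into the combination's summaries. The resulting dilution of objectives A and B cannot be quantified from the documents, because it depends on how many patients stop in the lead-in and on event rates that are not given.

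The timing gap is real but small: fewer than one of 8 lead-in samples is expected to be affected under either counting rule. That rests on the uniform-day assumption; if early cycle 2 starts are rare exceptions, the figure is lower still.

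**What to change.** - Reconcile 8.1 with 2.0, 7.1.2.7 and the Day 1 list in 7.1.4.2 on which expansion patients start with pembrolizumab alone, and state their number.
- Reconcile 7.1.2.7, the biopsy item in the visit list, 5.3.3 and the Day 1 list on the second biopsy's timing relative to the start of cycle 2. No dosing schedule is proposed here.
- State in the analysis plan that no sample taken after XL888 is classed as pembrolizumab-alone.
- In 8.4 and 8.6, tabulate lead-in cycle 1 adverse events, and any patient who never took XL888, separately from the combination's safety and activity results. State how the 80% rule applies when XL888 was held by design.

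The cost is wording and one extra table, with a slightly smaller denominator for the combination. No extra procedure or patient is needed.

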#### **Peripheral blood samples**

Approximately 10 mL of peripheral blood samples will be collected prior to initiation of study therapy, on day 1 of the first 3 cycles. The peripheral blood mononuclear cells will be isolated from these samples and stored in -80°C freezers until analysis. Samples will be evaluated for:

- i. Determine whether there is an increase in expression of T-cell co-stimulatory markers in PBMCs after treatment. Samples will be collected at baseline and every other week for the first 9 weeks. Analysis will include proportion of T, B, NK, memory and effector T cell subsets and expression of PD-1, PD-L1 and B7 family members.
- ii. Determine whether changes in ex vivo functional assays for PBMCs post treatment correlate with response. Samples will be collected at baseline and on weeks 6 and 9. This will be performed using interferon- gamma and CD107.

Shipping and handling instructions

After appropriate processing, the frozen samples will be sent to:

[name] Laboratory  
[name]  
[name]  
Winship Cancer Institute of Emory University  
[name]

Table 5 Laboratory Tests

Hematology	Chemistry	Urinalysis	Other
Hematocrit	Albumin	Blood	Serum $\beta$ -human chorionic gonadotropin†
Hemoglobin	Alkaline phosphatase	Glucose	( $\beta$ -hCG)†
Platelet count	Alanine aminotransferase (ALT)	Protein	PT (INR)
WBC (total and differential)	Aspartate aminotransferase (AST)	Specific gravity	aPTT
Red Blood Cell Count	Lactate dehydrogenase (LDH)	Microscopic exam ( If abnormal )	Total triiodothyronine (T3)
Absolute Neutrophil Count	Carbon Dioxide ‡	results are noted	Free tyroxine (T4)
Absolute Lymphocyte Count	( $CO_2$ or biocarbonate)	Urine pregnancy test †	Thyroid stimulating hormone (TSH)
	Calcium		
	Chloride		Blood for correlative studies
	Glucose		
	Phosphorus		
	Potassium		
	Sodium		
	Magnesium		
	Total Bilirubin		
	Direct Bilirubin ( If total bilirubin is elevated above the upper limit of normal )		
	Total protein		
	Blood Urea Nitrogen		
† Perform on women of childbearing potential only. If urine pregnancy results cannot be confirmed as negative, a serum pregnancy test will be required.			
‡ If considered standard of care in your region.			

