### **5.7.2 Subject Replacement Strategy**

Patients who do not complete the intended course of chemotherapy due to reasons other than toxicity will be considered as in-evaluable for the primary endpoint and will be replaced.

[illegible]

Trial Period:	Treatment Cycles a									End of Treatment	Post-Treatment		
Treatment Cycle/Title:	Main Study Screening (Visit 2)	1	2	3	4	5	To be repeated beyond 8 cycles			Discon	Safety Follow-up	Follow Up Visits b	Survival Follow-Up
Scheduling Window (Days):	-28 to -1	± 3	± 3	± 3	± 3	± 3	± 3	± 3	± 3	At time of Discon	30 days post discon ± 7 days	Every 8 weeks post discon	Every 12 weeks
Comprehensive Serum Chemistry Panel	X	X	X	X	X	X	X	X	X	X	X	X	
Fasting triglyceride, cholesterol and glucose	X			X				X					
Urinalysis	X			X				X		X			
T3, FT4 and TSH	X		X			X			X	X	X		
ECG g	X	X	X		X		X g		X g				
Tumor Imaging	X f			X h			X h						
Archival or Newly Obtained Tissue Collection i	X	X											
Correlative Studies Blood Collection j	X	X	X	X						X			

- Treatment cycles are 3 weeks
- Only for patients with ongoing treatment related toxicities
- Pembrolizumab will be given day 1, XL888 twice weekly orally
- ECOG performance status should be done within 10 days or less from day 1 of cycle 1
- Ophthalmologic exam done at baseline and repeated only if there are symptoms
- Baseline imaging with 8 weeks of day 1 is acceptable
- ECG day1 2 to 3 hours after administration of XL888 every other cycle after C2 (C1, C2, C4, C6 etc)
- Scans will be done every 3 cycles between day 15 and day 21
- Paired biopsies will only be obtained from 16 patients on the dose expansion cohort
- Samples will be collected at baseline, day 15, and every cycle for the first 9 weeks. Analysis will include proportion of T, B, NK, memory and effector T cell subsets and expression of PD-1, PD-L1 and B7 family members. Samples will be collected at baseline and on weeks 6 and 9. This will be performed using interferon- gamma and CD107.

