#### **7.1.4.2 Treatment Period**

##### **7.1.4.1 Day 1 ( $\pm 3$ days) of each cycle**

- Record concomitant medications
  - Vitals (temperature, HR, BP and RR)
  - History and physical exam, pill diary (prior cycle see section 11.4) and pill count (prior cycle)
  - ECOG performance status
  - Toxicity assessment
  - 12 lead ECG after XL888 administration in cycle 1, cycle 2 and every other cycle
    - Laboratory Assessments

- Hematology hemoglobin, hematocrit, red blood cell count, white blood cell count with differential and platelet count
  - Chemistry sodium, potassium, chloride, bicarbonate, magnesium, calcium, phosphorus, blood urea nitrogen, creatinine, glucose (random), total bilirubin, LDH, total protein, ALP, ALT, AST, and albumin
  - Tumor markers - when applicable
  - Fasting Lipid profile every 3 cycles starting Cycle 4 (i.e C4D1, C7D1, C10D1, C13D1 etc)
  - Urinalysis every 3 cycles starting Cycle 4 (i.e C4D1, C7D1, C11D1 etc)
    - T3, FT4, TSH cycle 2 and then after every 3 cycle
    - For the cycle 1 day 1 labs, blood samples from the screening tests maybe used if completed within 1 week of day 1
- Blood sample 20 cc for correlative work (only cycle 1, 2, 3)
  - Pembrolizumab 200 mg will be administered as a 30 minute IV infusion every 3 weeks. Given the variability of infusion pumps, a window of -5 minutes and +10 minutes is permitted (i.e., infusion time is 30 minutes: -5 min/+10 min).
- XL888 will be administered orally in the infusion center (first dose of each cycle only) prior to pembrolizumab. **(in selected case in patients receiving paired biopsies XL888 will be held in cycle 1)**

#### 7.1.4.2 Days 4, 8, 11, 15 and 18

- XL888 dose administered and diary completed

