#### **7.1.4.5 End of treatment visit**

- Record concomitant medications
  - Vitals (temperature, HR, BP and RR)
  - History and physical exam
  - ECOG performance status
  - Toxicity assessment
    - Laboratory Assessments
      - Hematology hemoglobin, hematocrit, red blood cell count, white blood cell count with differential and platelet count
      - Chemistry sodium, potassium, chloride, bicarbonate, magnesium, calcium, phosphorus, blood urea nitrogen, creatinine, glucose (random), total bilirubin, LDH, total protein, ALP, ALT, AST, and albumin
      - Tumor markers - when applicable
      - T3, FT4, TSH cycle 2 and then after every 3 cycle
- Blood sample 20 cc for correlative work

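### The T, B and NK populations in blood are planned only as proportions with no stated denominator, so a change in T-cell share cannot by itself be read as a change in T cells.

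*Combined protocol and SAP*

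**What the plan says.** Section 4.2.1.2 (Biomarker Research) gives the aim for blood: "We intend in all patients to evaluate the effects of the combination on T-cell population in peripheral blood".

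Section 7.1.2.7, Peripheral blood samples, has two items. Item i opens with "Determine whether there is an increase in expression of T-cell co-stimulatory markers in PBMCs after treatment" and then states the scale: "Analysis will include proportion of T, B, NK, memory and effector T cell subsets and expression of PD-1, PD-L1 and B7 family members". Item ii is a separate readout: "Determine whether changes in ex vivo functional assays for PBMCs post treatment correlate with response", using interferon-gamma and CD107. The flow-chart footnote in Section 6.0 repeats the scale for subset size: "Analysis will include proportion of T, B, NK, memory and effector T cell subsets".

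None of these places says whether a proportion is of mononuclear cells (PBMC), of lymphocytes or of T cells. Section 8.3 plans descriptive summaries of biomarker parameters and does not link them to the hematology results.

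The data needed for an absolute scale are partly in the plan. Table 5 lists an absolute lymphocyte count. The Day 1 visit list for each cycle includes "white blood cell count with differential and platelet count", and correlative blood is drawn on Day 1 of Cycles 1, 2 and 3. The end-of-treatment list has the same hematology together with "Blood sample 20 cc for correlative work". The list for Days 8 and 15 of Cycles 1 and 2 has correlative blood on Cycle 1 Day 15 but only chemistry among the laboratory tests.

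**The concern.** Shares of a whole sum to one. The T-cell share rises when B or NK cells fall, even if no T cell has been gained. It stays flat when all lymphocytes fall together. With no denominator stated, the reader also cannot tell whether monocytes enter the calculation.

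At stake is how the blood results are read. A shift in composition could be reported as a gain in T cells, or a real loss reported as no change, in a readout whose stated aim is the effect on the T-cell population.

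**Working it through.** The plan gives no figure to reproduce. Two checks apply: the arithmetic of a share, and the visits at which a count can be paired with a sample.

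**Share against count.** All cell counts here are assumptions, since the documents give none. Lymphocytes are taken as T + B + NK.

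- T share = T / (T + B + NK)
- T count = T share × absolute lymphocyte count (ALC)

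| Case | T / B / NK per microlitre | ALC | T share | T count | ln change in T count |
|---|---|---|---|---|---|
| Baseline | 1050 / 225 / 225 | 1500 | 1050/1500 = 70.0% | 1050 | – |
| B and NK halve | 1050 / 112.5 / 112.5 | 1275 | 1050/1275 = 82.4% | 1050 | 0 |
| T doubles | 2100 / 225 / 225 | 2550 | 2100/2550 = 82.4% | 2100 | ln 2 = 0.69 |
| All halve | 525 / 112.5 / 112.5 | 750 | 525/750 = 70.0% | 525 | ln 0.5 = −0.69 |

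The second and third cases give the same share, and the ALC tells them apart. The fourth case has the baseline share with half the T cells.

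**Range.** If the baseline T share is t and non-T lymphocytes are multiplied by f with T unchanged, the new share is t / (t + (1 − t)f).

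- f = 0.5: t = 60%, 70%, 80% becomes 75.0%, 82.4%, 88.9%. A doubling of T (1/f = 2) gives the same shares.
- f = 0.75: the same t becomes 66.7%, 75.7%, 84.2%. A 1.33-fold rise in T gives the same shares.

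**If the denominator is PBMC.** Add assumed monocytes of 400 per microlitre, doubling to 800 with lymphocytes unchanged. The T share goes from 1050/1900 = 55.3% to 1050/2300 = 45.7% with no T-cell loss. Multiplying by ALC alone would give 0.553 × 1500 = 829 and then 0.457 × 1500 = 685, a false fall of 17%. Multiplying by lymphocytes plus monocytes returns 1050 both times. The conversion must therefore match the denominator.

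**Pairing by visit, from the visit lists in Section 7.1.4.**

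| Correlative draw | Differential listed at the same visit? |
|---|---|
| Cycle 1 Day 1 | Yes, but the screening result may be used if taken within 1 week |
| Cycle 1 Day 15 | No, chemistry only |
| Cycle 2 Day 1 | Yes |
| Cycle 3 Day 1 | Yes |
| End of treatment | Yes |

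Four of five draws can be paired. Item i of Section 7.1.2.7 also mentions two-weekly draws through week 9, nominally Days 15, 29, 43 and 57. Day 1 visits fall on Days 1, 22, 43 and 64, so of those extra draws only Day 43 has listed hematology. The hematology row of the flow chart was not readable in the available text, so this check rests on the visit lists.

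**The case against.** The strongest reply is that item i opens with marker expression, and lineage proportions are only one component of it. That stands. A reader might infer that the blood immune results as a whole cannot be interpreted, and the documents do not support this. Expression on a defined subset, the interferon-gamma/CD107 assays, and memory/effector fractions gated within T cells do not depend on how many B cells, NK cells or monocytes are present.

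A reader might also infer that a misread share would reverse the exploratory hypothesis. Section 3.3 does not support that. Its hypothesis concerns the micro-environment and the response to PD-1 blockade. It does not predict a rise in circulating T cells, and no section plans a claim of T-cell expansion in blood.

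Thirdly, a matching count does not exist for every sample, and Cycle 1 Day 15, the first on-treatment draw, has none listed. This also stands and limits the fix.

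Other replies carry less weight. The plan's wording does not exclude counts, but none are planned. Section 8.6.1.2 summarises laboratory values by worst grade and change from baseline, so a marked fall in lymphocytes would show there, though not by lineage and not tied to the correlative samples. The analyses are descriptive and exploratory, which lowers the importance without making a share interpretable.

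**Conclusion.** The point holds for the T, B and NK shares. As specified, they cannot show whether T cells in blood rose or fell, and the missing denominator adds a second ambiguity. In the assumed example, a share of 82.4% is compatible with no change in T cells or with a doubling, and a share of 70.0% is compatible with no change or with a halving. The sizes depend on the assumed counts. That a share alone cannot separate these cases does not.

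It would go too far to say that lymphocyte counts are already collected alongside every correlative sample: the visit lists support this at four of five draws. The matter is minor. It affects the wording and scale of one exploratory, descriptive result and leaves the primary objective, the dose decision and the sample size untouched.

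**What to change.** In Section 7.1.2.7(i) and Section 8.3:

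- Define the denominator for T, B and NK proportions as lymphocytes. If shares of PBMC are reported, convert them with the lymphocyte plus monocyte count from the differential.
- Next to the proportions, report T, B and NK cells per microlitre (fraction of lymphocytes × absolute lymphocyte count) and the log change from baseline at Cycle 1 Day 1 (the baseline), Cycle 2 Day 1, Cycle 3 Day 1 and end of treatment.
- State that a change in share alone will not be described as a T-cell increase or decrease.
- Report Cycle 1 Day 15, and any other draw without listed hematology, as proportions only.

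The cost is SAP wording and one multiplication per lineage at four visits, with no added blood test. The proportions stay in the report, so nothing is lost. There are two downsides to state in the plan. The Cycle 1 Day 1 count may be up to 1 week older than the sample. Fractions from frozen PBMC multiplied by a fresh-blood count are approximate, because isolation and freezing may alter composition.
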